5.2 Secondary Endpoints

Secondary endpoints for this study are:

- Overall survival and event free survival 24 months post GTMP administration
- Immunoglobulin replacement therapies prior to and after gene therapy.
- Safety and tolerability.
- Performance outcomes and quality of life measured by the Karnofsky/Lansky scale and questions relevant to general well-being, school attendance and ability to practice sports, respectively.
- Severe infections or opportunistic infectious episodes, defined as infections or severe infections requiring hospitalization or prolonging hospitalization and/or documented infections by opportunistic pathogens (i.e. interstitial pneumonia, intractable diarrhoea).
- Response to tetanus vaccination.
- Immune reconstitution: T and B cell reconstitution.

5.3 Exploratory Endpoints

Exploratory endpoints for this study are laboratory correlates of efficacy that will be used to assess the level of gene correction, engraftment and immune reconstitution.

6 Timing of Analyses

The statistical analyses of efficacy data from this study will be performed in three stages:

- The first analysis will be carried out when a minimum of 5 subjects have completed 6-months follow-up post OTL-101 infusion. At this analysis, the success/failure of the OTL-101 cryopreserved infusion will be defined by the three criteria listed in the primary

objectives. This data will be compared with available data from UCLA ongoing Phase I/II study, treated with the OTL-101 fresh formulation. This will support the CMC comparability data between OTL-101 cryopreserved and fresh formulations. Secondary and exploratory endpoints will also be described and compared with the data from the fresh study.

- The second analysis will be carried out when all subjects have completed 12-months follow-up post GTMP administration. At this analysis, overall survival and event free survival will be evaluated. Secondary and exploratory endpoints, as well as baseline characteristics, subject disposition, and safety data will also be described.
- The third and final analysis will be performed to determine the overall survival and event free survival for all subjects 24 months post GTMP administration. Secondary and exploratory endpoints, as well as baseline characteristics, subject disposition, safety and busulfan pharmacokinetic (PK) data will also be described.

7 Analysis Populations

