2 PURPOSE OF THE STUDY AND STUDY OBJECTIVES

2.1 Purpose of the Study

The primary purpose of the study is to further explore the efficacy and safety of gene therapy with OTL-101, as an alternative treatment option for ADA-SCID patients. The current treatment of choice for ADA-SCID patients is a HLA-matched sibling/family HSCT, however the number of patients eligible for this procedure ranges from 10 to 20% (Hassan 2012). OTL-101 is a gene therapy that aims to use genetically modified autologous CD34+ HSC from the individual patients to improve the outcome of transplantation to a wider population. Two ongoing Phase I/II studies use a fresh cell formulation that is required to be infused within 6 hours of manufacture. A cryopreserved formulation of OTL-101 was developed to enable the treatment, once manufactured from the individual subjects' CD34+ cells, to be frozen and stored until the OTL-101 product is fully released (i.e. all quality control testing performed), allowing the subject to receive targeted conditioning prior to transplantation. The cryopreserved formulation will also permit the treatment to be shipped and delivered to a local expert site, thereby reducing the travel burden on the recipient and their family. The advantages of a cryopreserved formulation are not limited to shelf-life and include; an improved manufacturing process; improved quality of the OTL-101 product, thus allowing for all quality control tests to be performed and to permit standardisation of preconditioning regimens prior to OTL-101 infusion. Three subjects have already been treated with cryopreserved cells (with a different cryoprotectant as the one used under this protocol); two patients treated under Compassionate Use Program and one patient treated as an exemption in the US. All three subjects demonstrated immune reconstitution and are currently event free indicating success of the OTL-101 treatment.

Additionally, the purpose of this study is to support the analytical CMC comparability of the cryopreserved versus fresh OTL-101 formulation with an interim analysis of clinical outcomes from the five subjects, based on predictive parameters at 6 months of overall survival and event free survival: gene-marked granulocytes, ADA enzyme activity, and absolute CD3⁺ cell number.

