3.5 Duration of Subject Participation

The study will consist of the following periods:

- Screening: approximately 2 months
- Bone marrow harvest of autologous cells: 1 day
- Manufacture and release of OTL-101: 30-45 days
- Pre-conditioning prior to transplant: 4 days
- OTL-101 administration: this may entail up to 4-6 weeks of in-patient stay, either at UCLA or the subject may be transferred from UCLA to a home hospital at 3-7 days post-transplant for the pursuit of subsequent hospitalization for up to 4-6 weeks.
- Post treatment follow-up: 2 years after the administration of OTL-101.

The total study duration for each subject is estimated to be up to 2 years and 4 months.

The study will start when the first subject has signed the informed consent form. Each subject's participation in the study will end at the time of his/her last visit, or death. The study will have ended after the last subject has completed the last study visit at 24 months post OTL-101 infusion, however the primary endpoints for this study will be overall survival and event free survival at 12 months post OTL-101 infusion.

On completion of their participation in this study, subjects will be invited and encouraged to participate in a registry for long term data collection according to guideline recommendations.

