9.3.1 Primary Efficacy Endpoints

The primary efficacy endpoints for this study include treatment success at 6 months post OTL-101 infusion, and overall survival and event-free survival at 12 months post OTL-101 infusion.

Treatment success at 6 months post OTL-101 infusion, will be performed in support of CMC assessing comparability between cryopreserved and fresh formulations. Evaluation of the success of therapy will be based on the following parameters and their thresholds:

- a) Erythrocyte ADA enzyme activity above baseline/pre-treatment level (>0 Units),
- b) Absolute CD3+ T-cell counts $\geq 200/\text{mm}^3$, and
- c) Peripheral blood samples positive for vector sequences by qPCR($\geq 1/10,000$ cells).

Treatment will be deemed successful in subjects meeting all three above thresholds. These subjects will be designated as “responders”. Those subjects failing to meet at least one of the above thresholds will be considered to be “non-responders.”

Overall Survival is defined as the time-to death from the OTL-101 infusion if death occurred, or to the date of the last evaluation if death did not occur. If no death occurred, the subject’s data will be considered censored at the last evaluation.

Event Free Survival is defined as the time-to event from the OTL-101 infusion if an event occurred, or to the date of the last evaluation without an event if no event occurred. If no event occurred, the subject’s data will be considered censored at the last evaluation. Event is defined as any of the following:

- Death
- Returning to PEG-ADA ERT
- Need of rescue HSCT

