9.4 Sample Size Considerations

Due to the ultra-orphan nature of this indication, the sample size for this study is based on practical considerations. Specifically, the number of ADA-SCID patients expected to meet eligibility criteria yearly is around four to five. With a planned enrollment of three to six subjects per year, the sample size (N=10) for this study is considered reasonable.

It should be noted that the sample size will provide precision of 15% for 100% success (survival) at any particular time point. Precision is here defined as the half-width of the two-sided 95% CI using the Exact Binomial computations.

Ten subjects receiving OTL-101 will participate in this study.

Although all subjects will be evaluable for the first analysis at 6 months post OTL-101 infusion, the first five subjects will be reviewed to monitor the outcome of the study treatment. Sample size considerations for the first analysis of five subjects completing the 6-month follow-up assessment is based on realistic enrollment for this orphan indication. Experts in the field of HSCT and gene therapy use RBC ADA enzyme activity >0 U, absolute CD3+ T-cell counts $\geq 200/\text{mm}^3$, and peripheral blood samples positive for vector sequences by qPCR ($>1/10,000$ cells) as predictors of survival and event free survival and ultimately the success of the OTL-101 treatment. These parameters achieve plateau between 3 and 4 months post-intervention, therefore, a 6-month data cut for this interim analysis should be indicative of the final study outcomes.

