9.6 Statistical Methods

9.6.1 Overview

Full statistical methods will be detailed in the statistical analysis plan (SAP). The data will be summarized in tables displaying the mean, standard deviation, median, minimum, maximum and number of subjects for continuous data (e.g. age, weight) or in tables displaying count and percentage for categorical data (e.g. gender, previous treatment). Data will be presented by visit, if applicable.

All statistical analyses will be performed using Statistical Analysis System (SAS)® Version 9.4. or higher.

Statistical analyses will be performed, and their outcomes presented, in three stages:

1. The first (interim) analysis will compare the success/failure data 6-months post OTL-101 infusion. The success/failure of the OTL-101 cryopreserved formulation will be defined by the three criteria listed in the primary objectives ([Section 2.2.1](#)). This data will be compared with available data from the ongoing UCLA Phase I/II study using the OTL-101 fresh formulation. This will support the CMC comparability data between OTL-101 cryopreserved and fresh formulations. Secondary and exploratory endpoints will also be described.
2. The second (primary) analysis will determine the 12 month overall survival and event free survival for all subjects. Secondary and exploratory endpoints, as well as baseline characteristics, subject disposition, and safety data will also be described.
3. The third (final) analysis will be performed to determine the overall survival and event free survival for all subjects 24 months post OTL-101 infusion. Secondary and exploratory endpoints, as well as baseline characteristics, subject disposition, safety and Busulfan PK data will also be described.

This study is not designed to be powered to demonstrate statistical significance; therefore, no correction for overall Type I Error will be performed.

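### The 6-month responder composite is a primary endpoint, but its rate is scheduled only at a first analysis that may hold five subjects, and it has no exact confidence interval.

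*SAP*

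**What the plan says.** **Status of the endpoint.** Protocol 9.3.1 reads: "The primary efficacy endpoints for this study include treatment success at 6 months post OTL-101 infusion", followed by the 12-month survival endpoints. Protocol 2.2.1 and SAP 5.1 also make six-month response primary. Protocol 3.5 differs: "the primary endpoints for this study will be overall survival and event free survival at 12 months post OTL-101 infusion", with no mention of response. Protocol 9.6.1 labels the responder analysis interim and gives the word primary to the next one: "The second (primary) analysis will determine the 12 month overall survival and event free survival for all subjects".

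**When it is analysed.** The timing lists are in the protocol synopsis, Protocol 3.1 and 9.6.1, and SAP Section 6. Each names the composite and its comparison with fresh product at the first analysis only. The SAP sets the trigger: "The first analysis will be carried out when a minimum of 5 subjects have completed 6-months follow-up post OTL-101 infusion". For the second analysis it says: "At this analysis, overall survival and event free survival will be evaluated", then adds secondary, exploratory, baseline, disposition and safety data. The third analysis follows the same pattern at 24 months. Neither lists the composite.

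**Who is in the first analysis.** Protocol 2.1 ties the CMC support to the interim: "with an interim analysis of clinical outcomes from the five subjects". Protocol 11.6 locks the database for that interim on the first five subjects. Protocol 9.4 says "Although all subjects will be evaluable for the first analysis at 6 months post OTL-101 infusion, the first five subjects will be reviewed", and in its next sentence treats the first analysis as one of five subjects.

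**How it is summarised.** SAP 8.3.1.1 gives the number and percentage of responders, the same for each of the three criteria, and a descriptive comparison with the UCLA fresh-product study. No interval is planned. Protocol 9.6.4 and SAP 8.3.1.2 and 8.3.1.3 give overall and event-free survival an exact 95% interval. On precision, Protocol 9.4 notes that "the sample size will provide precision of 15% for 100% success (survival) at any particular time point".

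**The concern.** A primary endpoint should have a scheduled report on the full analysis population. Here the schedule gives the composite one report, and the trigger lets that report rest on half the planned cohort. The later lists do not pick it up: their references to secondary and exploratory endpoints do not cover a primary one.

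At stake are the responder rate and the comparison of cryopreserved with fresh product, which is the clinical support offered for the CMC comparability case. A result of 5/5 reported as 100%, with no interval, does not tell the reader that a true response rate near 48% remains compatible with it. The survival endpoints, reported for everyone with an exact interval, do not have this weakness.

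**Working it through.** **Inputs.** Planned N = 10, and precision defined as the half-width of the two-sided exact binomial 95% interval (Protocol 9.4). Smallest first analysis n = 5 (SAP Section 6; Protocol 2.1 and 11.6). No fresh-study counts are assumed.

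**Formula.** When all n subjects respond, the Clopper-Pearson upper limit is 1 and the lower limit L solves L^n = 0.025. So L = 0.025^(1/n), and the half-width is (1 − L)/2.

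**The plan's own figure.** For n = 10, L = 0.025^(1/10) = 0.6915 and the half-width is (1 − 0.6915)/2 = 0.154. The stated 15% is reproduced. A one-sided 95% limit would give (1 − 0.05^(1/10))/2 = 0.129, which does not match, so the two-sided reading is the right one.

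**At the first analysis.** For n = 5, L = 0.025^(1/5) = 0.4782 and the half-width is (1 − 0.4782)/2 = 0.261. The trigger is a minimum, so sizes in between are possible:

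| All respond | Lower 95% limit | Half-width (points) |
|---|---|---|
| 5/5 | 47.8% | 26.1 |
| 6/6 | 54.1% | 23.0 |
| 7/7 | 59.0% | 20.5 |
| 8/8 | 63.1% | 18.5 |
| 9/9 | 66.4% | 16.8 |
| 10/10 | 69.2% | 15.4 |

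**One non-responder.** The lower limit solves n·p^(n−1)·(1 − p) + p^n = 0.025, and the upper limit is 0.975^(1/n).
- 4/5 = 80%: 28.4% to 99.5%, half-width 35.6 points.
- 9/10 = 90%: 55.5% to 99.7%, half-width 22.1 points.

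**Would a five-subject trigger catch everyone anyway?** Protocol 9.4 plans three to six enrolments a year. At a steady pace, the five subjects after the fifth take 5/6 year (10 months) to 5/3 years (20 months) to enrol. A first analysis run when the trigger is met would therefore probably precede Month 6 for some of them.

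**The case against.** The strongest reply is that this rests on silence in timing lists. SAP 8.3.1.1 sets out the responder analysis with no five-subject limit, and the efficacy population is all treated subjects (Protocol 9.5.1, SAP 7.1). The protocol's own timing lists give no subject number for the first analysis, and the SAP says at least five. Protocol 9.4 can be read as keeping all subjects evaluable at six months and using the first five for monitoring. This stands in part: a ten-subject table is permitted. But none is scheduled, and Protocol 9.4 undercuts that reading in its next sentence.

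Second, failures would be visible elsewhere. SAP 8.1.2 summarises withdrawals and the later therapy of subjects in whom treatment failed, and disposition is scheduled at both all-subject analyses. The components are summarised by visit (SAP 8.3.2.6, 8.3.3.5, 8.3.3.6). This also stands, and it narrows the gap. A reader might infer that failures among the later subjects would go unreported, and the documents do not support that. What is missing is the responder rate itself and its comparison with fresh product.

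Third, the study is descriptive and unpowered (Protocol 9.6.1, 9.6.4). That is correct, so type I error is not at issue. A descriptive interval fits this framework, since the survival endpoints already have one.

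Four further inferences are tempting but unsupported:
- That only a percentage would be shown. SAP 8.3.1.1 gives the count as well, and each criterion separately.
- That N = 10 was chosen for its half-width. Protocol 9.4 bases it on practical considerations and only notes the precision.
- That unmeasured subjects are already non-responders by definition. SAP 5.1 speaks of subjects not meeting criteria, not of subjects without a value.
- That the interim denominator should be everyone whose Month 6 date has passed. SAP Section 6 requires completed six-month follow-up, and the visit window is ±2 weeks, so a subject with a visit still pending could be miscounted.

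**Conclusion.** The point holds as a gap in the reporting of one primary endpoint; it does not extend to all efficacy results. Followed as written, the only scheduled responder rate, and the only scheduled comparison with fresh product, could come from five of ten subjects and carry no interval. In the best case, moving from five to ten subjects raises the lower limit from 47.8% to 69.2% and cuts the half-width from 26.1 to 15.4 points. The 15% noted in Protocol 9.4 is correct for ten subjects and does not apply to a five-subject result.

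These figures assume the exact two-sided 95% interval that Protocol 9.4 itself uses, and all-responder results unless stated. They assume that the first analysis runs at the minimum; a larger first analysis shrinks the gap as the table shows. The change should be made: the Month 6 responder assessment is already scheduled for every subject (Protocol Table 2), so the precision is available from data being collected.

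**What to change.** 1. In SAP Section 6 and Protocol 3.1 and 9.6.1 (and the matching synopsis text), add to the second (12-month) analysis the 6-month responder number and percentage for all treated subjects, with its descriptive comparison with the fresh study. Label the five-subject result as interim.
2. In SAP 8.3.1.1, add a Clopper-Pearson 95% confidence interval for the responder proportion.
3. Reconcile Protocol 9.4 with Protocol 2.1, Protocol 11.6 and SAP Section 6 on who is in the first analysis.
4. Reconcile Protocol 3.5 with Protocol 2.2.1 and 9.3.1 on whether the composite is primary.

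The cost is wording in both documents, one extra table at the second analysis, and an interim result whose precision looks less favourable. No new data are needed.

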7.1 Efficacy Population

The efficacy population will be a modified intent-to-treat population including all subjects treated with OTL-101 within this protocol.

7.2 Safety Population

The safety population will consist of all subjects treated with OTL-101 within this protocol.

8 Statistical Methods

In general, continuous variables will be summarized using the mean, standard deviation, minimum, median, maximum and number of subjects. Categorical variables will be summarized using number of subjects and percentages.

8.1 Subject Disposition

8.1.1 Summary of Populations

Number and percentage (%) of subjects enrolled, treated, and in efficacy and safety populations will be summarized. The denominator for the percentages will be the number of subjects enrolled.

8.1.2 Summary of Withdrawals

Number of subjects enrolled, number treated, number (%) of subjects who completed the study period will be summarized along with the reason for withdrawal. The denominator for the percentages will be the number of subjects treated.

For subjects in whom the treatment failed, the number (%) who had a second gene therapy, a rescue HSCT or other therapy will be summarized, the denominator will be the number of subjects who failed treatment.

8.2 Demography and Baseline Characteristics

Demography and baseline characteristics will be summarized for the safety population.

8.2.1 Demography

Age in months will be calculated as:

$$12 * (\text{date informed consent signed} - \text{date of birth}) / 365.25.$$

Age, weight and height at screening will be summarized using descriptive statistics.

Sex, race, ethnicity and location will be summarized using the number (%) of subjects in each category.

8.2.2 Medical History

The number (%) of subjects reporting medical history will be summarized overall and by category.

8.2.3 Diagnosis of ADA-SCID

First symptoms and primary diagnosis will be summarized using the number (%) of subjects with each symptom/diagnosis.

Age at symptom onset and age at diagnosis in months will be calculated as

$$12 * (\text{date of onset/diagnosis} - \text{date of birth}) / 365.25.$$

Age at symptom onset and age at diagnosis in months will be summarized using descriptive statistics.

8.2.4 Disease Treatment History

The number (%) of subjects previously receiving PEG-ADA ERT, immunoglobulin therapy, prophylactic agents and other therapies will be summarized.

The number (%) of subjects with a previous transplant, type of transplant cells, donor type and outcome will be summarized.

Time since transplant in months will be calculated as

$$12 * (\text{date informed consent signed} - \text{date of transplant}) / 365.25.$$

8.2.5 Cytogenetics

Cytogenetics will be assessed at screening and categorised as normal or abnormal.

The number (%) of subjects falling into each category for type of test, source and result (normal/abnormal) will be summarized.

8.2.6 Coagulation Tests

Coagulation tests (prothrombin time (PT), partial thromboplastin time (PTT) and internal normalised ratio (INR)) will be evaluated over time prior to the OTL-101 infusion.

For each parameter, the actual value will be summarized at each visit using descriptive statistics.

Coagulation tests will be flagged against the normal range as low/normal/high. For each parameter, the number (%) of subjects with evaluations that were low/normal/high relative to the normal range will be summarized by visit. Out of range values will be assessed for their clinical significance. For each parameter, the number (%) of subjects with clinically significant evaluations will be summarized by visit.

8.2.7 Urinalysis

Urinalysis tests (pH, glucose, ketones, protein, bilirubin, blood, urobilinogen, nitrites, leukocytes, specific gravity) will be evaluated over time prior to the OTL-101 infusion.

The urinalysis evaluations are assessed as ‘Normal/Negative’ or ‘Abnormal/Positive’. If any urine cultures are taken, the results will be categorized as ‘positive’, ‘negative’ or ‘mixes’. These data will be listed.

8.2.8 ECG

An ECG will be taken at screening.

RR interval, PR interval, QRS interval and QT interval will be summarized using descriptive statistics.

The ECG will be categorised as ‘normal’/ ‘abnormal, not clinically significant’/ ‘abnormal, clinically significant’. The number (%) of subjects with evaluations falling into each category will be summarized along with the number (%) with each type of abnormal finding.

